2.1 Objectives & Hypotheses	
Hypothesis: The development of alternative methods of screening for HCV infection in persons who inject drugs (PWID), as part of a harm reduction strategy at “Cañada Real” shantytown (Madrid), may facilitate diagnosis of the disease in this population, increase the frequency of referral to hospital and administration of appropriate HCV treatment and thus reduce the prevalence of HCV.
 
Objectives: The overall objective of this project is to evaluate whether the implementation of an alternative method of HCV screening in PWID from "Cañada Real " (Madrid) can improve the localization of HCV-infected patients for subsequent referral to the Hospital, administration of HCV antiviral therapy and cure of hepatitis C. The effectiveness of the intervention in each of the phases of the project will be assessed.
 
Main objectives:
 
 1. To develop and validate an alternative method of screening for active hepatitis C virus (HCV) infection based on collection of capillary blood via finger pricking and Whatman™ cards (dried blood). 2. Implementation of a screening program in PWID from "Cañada Real" (Madrid) aimed at early HCV detection (diagnostic) and early HCV treatment as part of a harm reduction strategy, and 3. To assess the effectiveness of our alternative HCV screening test in PWID through evaluation of the impact on the patients' health (referrals to health centers, number of treated patients, and the percentage of cure). 
Secondary objectives:
 
 4. Estimation of the prevalence of HVC active infection or HCV resolved spontaneously with the methodology developed. 5. To estimate the prevalence of other chronic viral infections (eg, HIV, HBV, and HDV) that are relatively common in PWID. 6. To estimate the prevalence of active HCV infection 24 months after the first intervention in “Cañada Real”. 7. To assess factors associated with HCV infection and transmission through an epidemiological survey, which will collect demographic data and risk behaviors.

**2.2
Background &
Rationale,
Significance of
Selected
Topic &
Preliminary
Data**

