HCV infection is a major health problem worldwide. The main source of infection is currently parenteral drug use, especially in more developed countries. HCV infection is the main cause of liver-related death and the principal indication for liver transplant in industrialized countries. Increased knowledge of the molecular mechanisms involved in the cell cycle of HCV has made it possible to develop a new family of drugs known as direct-acting antivirals (DAAs). Treatment courses are now short and very safe. In addition, dosing is convenient and efficacy and cure rates are high.

Spain has one of the highest HCV infection prevalence values in Europe. The estimated prevalence of HCV antibodies is 1.7%, and the prevalence of positive viral load in adults is 1.2%, that is, 472,000 adults with active infection. However, it is estimated that only 40% of HCV-infected persons in Spain have actually been diagnosed, probably because conventional screening strategies have not been widely applied and have proven to be of limited efficiency both in the general population and in hard-to-access risk groups. Despite the extent of this health problem, the true prevalence of HCV infection in our area is not known. The recently established National Hepatitis C Plan opened a line of investigation aimed at quantifying the problem, describing the epidemiological characteristics of those infected, and establishing preventive measures. The National Hepatitis C Plan, which came into force on April 1, 2015, has been a definite boost in the treatment of hepatitis C in Spain. In the first year of the Plan, more than 40,000 patients with HCV have been treated, acquiring similar cure rates to those reported in clinical trials. HCV therapy in Spain is widely available and PWID are considered to be a priority population.

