PWID are at high risk from blood-borne infections, including human immunodeficiency virus (HIV) and HCV through the sharing of needles and injection equipment. Harm reduction refers to policies, programs and practices that aim to reduce the harms associated with the use of drugs in people unable or unwilling to stop. Harm reduction began to be discussed frequently after the threat of HIV spreading among and from PWID was first recognized. However, similar approaches have long been used in many other contexts for a wide range of drugs. There is persuasive evidence from the literature that harm reduction approaches greatly reduce morbidity and mortality associated with drug use and combined prevention measures (Needle and syringe programmes & opioid substitution therapy) contribute to the reduction of the spread of

HIV and HCV infections. Although there is concern that HCV re-infection may negate the potential benefits of treatment, the reported rates of reinfection following successful HCV treatment among PWID are low, especially when combining high coverage of harm reduction measures.

Cañada Real is a major shantytown on the outskirts of the city of Madrid. It is estimated that 90% of the illegal drugs in the Madrid region are sold and consumed in Sector VI of Cañada Real and that between 4000 and 6000 people per day go to this shantytown for their drug doses. The Anti-Drug Agency (Agencia Antidroga) runs a daily mobile unit in the area as a harm reduction strategy. The remit of the unit is to minimize damage from drug consumption by taking health-related, psychological, and social measures. It deals mainly with outreach drug consumers (individuals who are outside the reach of the health system and have great difficulty accessing it). This harm reduction unit identifies drug users at risk, offering them needles, syringes, opioid substitution therapy and screening for HIV and HCV. When a PWID tests positive for HIV or HCV, he is referred to Infanta Leonor Hospital for appropriate therapy. The harm reduction team accompanies the drug user to hospital and ensures his follow-up and adherence to therapy. Recent hepatitis C test and care programs have identified the use of patient navigators or care coordinators to be an important intervention in overcoming challenges to linkage to and retention in care

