Participants will be given an information leaflet and a specific informed consent form. Samples will be processed according to the study protocol (Annex 1). Clinical and epidemiological data will be recorded in a database that can be accessed by researchers from the HUIL and the CNM-ISCIH. The variables shown in section 2.4 will be recorded. This file has been included in the Register of Data Files of the ISCIH.

ELISA: A disc with a sample of dried blood will be placed in a microtube containing 300 μl of 0.5% buffer solution (PBS/BSA) and processed at $4-8^{\circ}\text{C}$ for 18-24 hours. After incubation, elutes from the dried blood samples will be tested for the presence of antibodies against HCV, HIV, and HDV, as well as for HBV surface antigen (HBsAg). Negative samples will not undergo further testing and will be considered non-infected. Positive samples will be tested using real-time PCR to confirm the positive results.

Real-time PCR: Nucleic acids will be extracted using the DSP virus pathogen kit (QIAGEN, Hilden, Germany). The samples will be stored at -80°C until use. A specific HCV test will be performed to confirm active HCV infection (HCV-RNA positive) on a Rotor Gene Q unit (QIAGEN).

PHASE II: SCREENING AT CAÑADA REAL GALIANA

Screening for HCV and the other viruses (HIV, HBV, and HDV) covered by this project will take place at Cañada Real Galiana. Screening will be conducted by nursing personnel hired specifically for that purpose. An active search will be made for

individuals who come into the shantytown from outside, and the detection test will be offered to everyone regardless of whether or not their serological condition is already known. Selection of individuals for screening will be random and consecutive.

Nursing personnel will generally be accompanied by an educator from the HRU. PWID will be offered information on prevention and the importance of early diagnosis and referral to health centers.

Information will then be provided on the goals of the study, and persons who agree to take part will be required to sign an informed consent form, provide contact data for subsequent location, and provide basic social and demographic data and information on their consumption habits. Regardless of whether or not individuals agree to take part in the study, they will all be given a card containing basic information on prevention and contact data for the internal medicine department of HUIL and the HRU.

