2.6 Study Duration

2.7 Statistical Analysis and Sample Size Justification

PHASE I

Once all subjects have been included, the results from the Whatman 903 cards will be compared with those obtained by venipuncture at HUIL. Diagnostic performance will be assessed by calculating the area under the ROC curve (AUROC) for each virus. The Se, Sp, PPV, and NPV for each virus will also be calculated.

PHASE II

Sample size: Assuming that around 10,000 people visit Cañada Real Galiana on different days, a sample size of 930 randomly selected subjects will suffice to estimate, with a 95% confidence interval and a precision of ± 3 percentage points, a

population percentage considered to be around 60%. A replacement rate of 0% has been anticipated.

PHASE III

In order to evaluate the effectiveness of the intervention, the accuracy of HCV tests will be calculated at the population level (AUROC, Se, Sp, PPV, and NPV), as will the percentage of patients arriving at the clinic, the percentage of patients treated, and the percentage of patients cured of hepatitis C. The incidence of HCV reinfection will be assessed using a Kaplan-Meier survival method. In addition, the effectiveness of the intervention for HIV, HBV, and HDV infection will be evaluated.

Statistical Methods

The statistical analysis will be performed using IBM SPSS Statistics for Windows, Version 22.0 (IBM Corp, Armonk, New York, USA) and the R statistical package, version 3.2.2 (GNU General Public License). All tests will be two-tailed, with p-values of <0.05 considered statistically significant.

An assessment will be performed to determine the percentage of patients who are positive at screening, are referred to a health center, have their diagnoses confirmed, and are treated at the end of the study. Factors associated with virus transmission, lack of referral to a health center, and HCV treatment will also be analyzed.

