Continuous variables will be presented as mean and standard deviation; categorical data will be presented as absolute numbers and percentages. The prevalence (95% confidence interval) of antibody for HCV, HIV, and HDV, HBsAg, and active HCV infection will be calculated in the sample and in the subgroups studied. Categorical data and proportions will be analyzed using the chi-square test or Fisher exact test, as required. The *t* test, ANOVA, or Mann-Whitney test will be used to compare continuous variables. The association study will be performed using logistic regression and adjusting for the major epidemiological and clinical covariates.

VARIABLES INCLUDED

PHASE I: VARIABLES TO BE RECORDED DURING INTERNAL VALIDATION TESTING

- Date of birth
- Gender
- Date of sample collection
- Date of last analysis
- HCV antibody result from last analysis (positive/negative)
- HCV-RNA result from last analysis
- Genotype result from last analysis
- HIV antibody result from last analysis (positive/negative)
- CD4+ lymphocyte count for HIV-positive patients
- RNA-HIV result for HIV-positive patients
- HDV antibody result from last analysis (positive/negative)
- HBsAg result from last analysis (positive/negative)
- DNA-HBV result from last analysis
- Incidents or errors in sample collection (yes/no)

PHASE II: VARIABLES TO BE RECORDED DURING SCREENING

- Code allocated
- Date of sample
- Date of birth
- Gender (male/female)
- Nationality
- Homeless (yes/no)
- No. of days per week that the individual visits Cañada Real Galiana
- Drugs consumed (mark as relevant):
 - Heroin
 - Cocaine
 - Marihuana
 - Alcohol
 - Benzodiazepines
- Current use of parenteral methods (yes/no)
- Date when parenteral methods were first used
- Frequency of injections (daily [No. of times]/weekly [No. of times])
- Syringe sharing for >3 months (yes/no)
- Frequency of syringe sharing (daily/weekly/monthly)
- Date of switch from parenteral methods to smoking
- On methadone program (yes/no)
- Being monitored for HCV infection (yes/no)
- Have you previously been offered the chance to undergo HIV and/or HCV testing?
 - No
 - Yes, but I did not accept
 - Yes, with (positive/negative) results for HIV and (positive/negative) results for HCV
- Contact with health center (never, occasionally, regular monitoring).
 - Primary health care
 - Hospital
 - Drug abuse center
 - Other
- Advantages of alternative screening
- Drawbacks of alternative screening
- Contact data provided (yes/no)

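### Prior HCV treatment is not recorded, so cured and spontaneously resolved infection cannot be separated; HCV monitoring is recorded, but the Phase III percentages are not broken down by it

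*Combined protocol and SAP*

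**What the plan says.** **Objective and test.** Secondary objective 4 in Section 2.1 is "Estimation of the prevalence of HVC active infection or HCV resolved spontaneously with the methodology developed". The laboratory steps in Section 2.3 are an antibody ELISA on the card eluate, then real-time PCR only for positive samples. Section 2.7 (Statistical Methods) lists prevalences for HCV, HIV and HDV antibody, HBsAg and active HCV infection. It lists no resolved category, and the term in objective 4 is not defined anywhere.

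**Who is tested.** In Phase II (Section 2.3), "the detection test will be offered to everyone regardless of whether or not their serological condition is already known".

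**Care that already exists.** Section 2.2 says that in the first year of the national plan "more than 40,000 patients with HCV have been treated", with cure rates like those in trials, and that people who inject drugs are a priority group. It also describes the harm reduction unit's current practice: "When a PWID tests positive for HIV or HCV, he is referred to Infanta Leonor Hospital for appropriate therapy".

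**What is recorded.** The Phase II variables in Section 2.7 include an item that begins "Being monitored for HCV infection (yes/no", a question on previous offers of testing with the reported results, and the level of contact with primary care, hospital and drug services. Antiviral treatment appears only in the Phase III list, after referral and the hospital results.

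**What is analysed.** Section 2.7 (Phase III) gives the percentages arriving at the clinic, treated and cured. It states no exclusion or breakdown by earlier diagnosis or care. Factors associated with non-referral and with treatment are to be analysed, with logistic regression adjusted for covariates that are not named.

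**The concern.** There are two separate gaps, one in data collection and one in analysis.

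First, an antibody-positive, RNA-negative result shows that the infection is no longer detectable. It does not show why. Where treatment is widely available, some of these people may have been cured by drugs. If the category is reported as spontaneous resolution, each of them adds to the estimate, and the error can go in only one direction.

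Second, the overall objective in Section 2.1 is whether the alternative screening can improve the localization of infected people for referral, treatment and cure. A person already followed for HCV, perhaps at the same hospital, was not located by the card. Counting such people together with the newly found gives a percentage that does not describe what the screening added.

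**Working it through.** **1. The plan's own figure.** Section 2.7 states for Phase II that "a sample size of 930 randomly selected subjects will suffice to estimate" the target percentage. Its inputs are an expected value near 60%, a half-width of 3 points at 95% confidence, and a source population of about 10,000.

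- n0 = 1.96² × 0.60 × 0.40 / 0.03² = 1024.4
- With finite population correction: 1024.4 / (1 + 1023.4/10,000) = 929.3, rounded up to 930.

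The figure reproduces. The point below concerns classification and attribution, so no sample size changes.

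**2. Can any listed variable identify earlier cure?**

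- Previous testing: a spontaneous resolver and a cured patient can both report an earlier positive HCV result.
- Current monitoring: this misses someone cured and discharged.
- Antiviral treatment (Phase III list): it follows referral and has no item for treatment before screening.
- Medical history at the first hospital visit: it covers only people who attend, and prior treatment is not a listed variable.

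None of them separates the two groups.

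**3. Size of the misclassification (assumed inputs).** Let A be antibody prevalence and t the share of antibody-positive people cured before screening. The overstatement in prevalence is A × t. The plan does not say whether its 60% is antibody or active infection. Here A = 60% is assumed to be antibody, so 0.60 × 930 = 558 people. For the reported resolved prevalence, take the RNA-negative share among antibody-positives from the national figures in Section 2.2: 1 − 1.2/1.7 = 29.4%, so 0.60 × 29.4% = 17.6%.

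| t (assumed) | People misclassified | Overstatement | Reported | Spontaneous |
|---|---|---|---|---|
| 5% | 28 | 3.0 points | 17.6% | 14.6% |
| 10% | 56 | 6.0 points | 17.6% | 11.6% |
| 15% | 84 | 9.0 points | 17.6% | 8.6% |

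A rough national anchor for t: 472,000 viraemic adults at 1.2% imply 472,000 × 1.7/1.2 = 668,667 antibody-positive, of whom 196,667 are RNA-negative. If 40,000 viraemic people were treated and all were cured, t = 40,000/668,667 = 6.0%, and cured people make up 40,000/(196,667 + 40,000) = 17% of the RNA-negative group. With A = 60% the overstatement would be 0.60 × 6.0% = 3.6 points. This assumes that the prevalence figures predate the national plan, ignores earlier cures, and applies a national rate to this population.

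**4. Size of the attribution problem (assumed inputs).** Let m be the share of positives already in care, c the share of them counted as linked, and L the linkage among the rest. The reported percentage is m × c + (1 − m) × L, so it exceeds L by m × (c − L). With c = 90% and L from 70% down to 30%:

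- m = 10%: 2 to 6 points
- m = 20%: 4 to 12 points
- m = 30%: 6 to 18 points

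The sign depends on c exceeding L. With m = 20%, c = 50% and L = 70%, the difference is 0.20 × (0.50 − 0.70) = −4 points.

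**The case against.** **Earlier care is collected.** A reader might infer that the plan ignores it. It does not: monitoring, previous testing with results and contact with services are all Phase II variables, and factors associated with referral and treatment are to be analysed. This stands. For the Phase III percentages the gap is only that no rule splits them by these items, and that can be remedied from data already planned.

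**The label is never defined.** That cured people will be counted as spontaneous is an inference, because objective 4 is not turned into a category anywhere. This is fair, but antibody-positive, RNA-negative is the only resolved category that the method can supply.

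**Correction later is possible.** A reader might conclude that the error could never be undone. Section 2.3 makes the study hospital the reference centre for the shantytown and says that people diagnosed there are referred to it, so its records should show some earlier treatment. They would be incomplete: Phase II seeks people who come from outside and may have been treated elsewhere, and the registry search in Phase III is described only for finding positives who cannot be contacted.

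**The effect may be small.** Section 2.2 describes a population largely outside the health system, which argues for few earlier cures. The same section calls it a priority group for treatment. The documents do not settle this.

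**Known patients can be a programme success.** Accompaniment and treatment support are part of the intervention, so bringing back someone known but untreated can be a real effect. Also, monitored people who have been cured are RNA-negative and leave an RNA-positive denominator, so high treatment rates among those still viraemic cannot be taken for granted. This is why known but unmonitored people should stay in, and why a breakdown is preferable to an exclusion.

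**Conclusion.** The point holds in two limited parts.

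1. The prevalence of spontaneously resolved HCV cannot be estimated with the variables listed. Any earlier cure inflates it. The direction is certain, but the size is not known. An overstatement of 3 to 9 points follows from an assumed 60% antibody prevalence and an assumed 5% to 15% cured earlier. At 5% it already equals the ±3 points of precision planned for the main percentage. This affects half of one secondary objective. The estimate of active infection is untouched.
2. The Phase III percentages mix new linkage with existing care. The difference could be a few points or more than ten under the assumed inputs, and its sign depends on whether people already in care are linked more often than the rest.

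A reader might go further and say that the overall percentages are inflated by a known amount, or that the overall objective cannot be answered. The documents support neither. They give no share already cured or in care, they plan descriptive percentages, and the items needed for a useful breakdown are collected.

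**What to change.** **Before Phase II starts**

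- Add one variable: *Ever treated for hepatitis C? (yes/no, year, outcome)*. Where consent allows, check it against hospital records.
- In objective 4 and Section 2.7, name the category antibody-positive, RNA-negative. Report it as spontaneous resolution only among people never treated.

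**In the Phase III analysis**

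- Keep the overall percentages referred, confirmed, treated and cured.
- Report them also for three groups defined by items already listed: newly diagnosed (no earlier positive HCV result reported, not monitored), known but not monitored, and already monitored.
- Base statements about improved localization on the first two groups, and describe them without a comparative claim.

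**Cost.** One extra self-reported question, open to recall error, and a few lines of analysis text. The subgroup denominators are smaller, so their confidence intervals will be wider. The sample size of 930 does not change. If the question cannot be added, relabelling the category alone removes the mislabelling, but the spontaneous estimate is then given up.

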
protocol.

The Whatman 903 cards used to collect whole blood will be handled by healthcare professionals. The device consists of a small card with five circles for collecting one drop of blood each. The card is attached to a record card where demographic information on the individual being tested is recorded. A small amount of capillary blood from the user's ring or middle finger is collected on the sample collection area and then allowed to dry at room temperature for three hours. The card is then made ready for transportation to the screening laboratory. It must be taken to the laboratory within 15 days of collection.

Samples will be sent to the CNM-ISCIH for laboratory testing. The cards will be stored at -80°C .

PHASE I: INTERNAL VALIDATION AND REFINING OF THE TECHNIQUE

Once the ethics committee has approved the study, samples will be obtained by finger pricking using Whatman 903TM cards at visits to the Internal Medicine department of HUIL. All patients visiting the department, for whom recent analytical data (serology results for HCV, HIV, HBV, and HDV, as well as HCV-RNA viral load and HCV genotyping collected during the previous 15 days) will be asked to take part in the internal validation study. Patients whose analyses were performed elsewhere or are not recent will not be included. Healthy individuals, i.e. those who have tested negative for HCV, HIV, HBV, and HDV will also be included. Individuals will be included in the validation consecutively until the preset number is reached (see below).

A total of 100 patients and 50 healthy individuals will be included to validate the screening test. Successive samples will be taken, and patients with genotypes 1a, 1b, 2, 3, and 4 will be included. National data indicate that the distribution of the most frequent genotypes in Spain is as follows: 1b, 44%; 1a, 26%; and 3, 20%. Therefore, these will be the genotypes most widely represented in our study. The 50 healthy individuals (negative for HIV, HBV, HCV, and HDV) will be obtained from the family members accompanying patients on medical visits, who will be invited to take part in the study. One dried blood sample will be taken by finger pricking and another simultaneous sample will be taken by venipuncture. The venipuncture sample will be processed through the usual channels at the center.

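### Phase I promises card accuracy for four viruses but secures no HIV, HBsAg or anti-HDV positives, so sensitivity would probably be very imprecise for HBsAg and may not be estimable for anti-HDV

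*Combined protocol and SAP*

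**What the plan says.** Section 2.3 (Phase I) sets the size of the validation sample: "A total of 100 patients and 50 healthy individuals will be included to validate the screening test". The patients are those attending the hospital's internal medicine department who have recent serology for HCV, HIV, HBV and HDV, "as well as HCV-RNA viral load and HCV genotyping collected during the previous 15 days". It adds that "Patients whose analyses were performed elsewhere or are not recent will not be included". The make-up of the patient group is described only by HCV genotype: "patients with genotypes 1a, 1b, 2, 3, and 4 will be included".

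On controls it says: "Healthy individuals, i.e. those who have tested negative for HCV, HIV, HBV, and HDV will also be included". On recruitment: "Individuals will be included in the validation consecutively until the preset number is reached". No group, quota or minimum is given for patients positive for HIV, HBsAg or anti-HDV.

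For Phase I, section 2.7 plans an AUROC for each virus and then states: "The Se, Sp, PPV, and NPV for each virus will also be calculated". The Phase I variable list in the same section includes reference results for HIV antibody, HDV antibody and HBV, for example "HBsAg result from last analysis (positive/negative").

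**The concern.** A sensitivity needs reference-positive subjects. An HCV genotype can be obtained only from someone with detectable HCV-RNA. If every Phase I patient must have one, a patient with HIV or HBV but no HCV does not qualify, although that patient would supply a positive for those assays. The controls supply none. Positives for three of the four viruses then arise only by chance co-infection.

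The estimates matter beyond Phase I. Section 2.3 bases the Phase II field screening for HIV, HBV and HDV on the Phase I laboratory results. The ELISA paragraph in 2.3 stops testing after a negative card result and counts that person as uninfected. Only card-positive people are offered hospital confirmation, so missed infections are not systematically sought. Secondary objective 5, the prevalence of HIV, HBV and HDV, would rest on card assays whose sensitivity might be unknown.

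**Working it through.** **Inputs from the documents.** 100 patients and 50 controls negative for all four viruses (2.3). Sensitivity and AUROC for each virus (2.7). A previously published sensitivity of 94% for the card (2.3, limitations). The documents give no derivation of 100 + 50, so there is no plan figure to reproduce for Phase I.

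**Inputs assumed.** Co-infection rates among the 100 patients: HBsAg 1% to 5%, with 10% as a high value; anti-HDV 0.5% to 1%; HIV 10% to 30%.

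**Formulas.** Expected positives = 100 × p. Chance of no positive = (1 − p)^100. If all n positives are detected, the exact (Clopper-Pearson) two-sided 95% lower limit for sensitivity is 0.025^(1/n).

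**HBsAg**

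| Assumed p | Expected positives | Chance of none | Lower limit if all detected |
|---|---|---|---|
| 1% | 1 | 0.99^100 = 37% | 2.5% (1/1) |
| 2% | 2 | 0.98^100 = 13% | 16% (2/2) |
| 5% | 5 | 0.95^100 = 0.6% | 48% (5/5) |
| 10% | 10 | <0.01% | 69% (10/10) |

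**Anti-HDV.** At 0.5%, the chance of no positive is 0.995^100 = 61%. At 1% it is 37%. With no positive, sensitivity and AUROC are undefined. The result is sensitive to the assumption. If HDV is instead taken as 5% to 50% of HBsAg positives, with HBsAg at 1% to 10%, expected positives run from 0.05 to 5 and the chance of none from 95% to 0.6%.

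**HIV.** At 10% to 30%, 10 to 30 positives are expected, with lower limits of 69% (10/10) to 88% (30/30).

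**HCV, for comparison.** 94 detected of 100 gives 87.4% to 97.8%.

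**Specificity.** With 5 HBsAg positives, 150 − 5 = 145 subjects remain as negatives, so specificity is well supported.

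**Positives needed, for scale.** At 94% sensitivity, n = 1.96² × 0.94 × 0.06 / d². This gives 22 positives for d = ±10 points, 45 for ±7 and 87 for ±5 (normal approximation).

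**The case against.** A reader might infer that patients without HCV cannot enter and that sensitivity for HBV and HDV cannot be derived. The documents do not support either statement in that form.

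- The eligibility sentence lacks a verb. Its parenthesis can be read as a cumulative requirement or as a list of data types, and no sentence expressly excludes patients without HCV. The genotype description favours the cumulative reading without settling it. On the looser reading, there is still no planned number of positives for three viruses.
- Co-infected patients are eligible and their HBsAg and HDV antibody results are recorded. One positive makes sensitivity calculable. At the assumed rates, the chance of at least one HBsAg positive is 63% to 99.4%.
- NPV can be computed even with no positives, although it would then say nothing useful.
- Figure 2.4.1, on the internal validation, is not available here, so the absence of a minimum can be stated only for the visible text.
- Phase III records hospital HIV antibody and HBsAg results. People referred for HCV but card-negative for HIV or HBsAg would give some paired data. This is partial relief: section 2.7 plans population-level accuracy for the HCV tests only, and no hospital HDV antibody result is listed.
- Validation for active HCV is main objective 1, and the other viruses belong to a secondary objective. Concentrating on HCV genotypes is a reasonable priority, and any minimum for other viruses competes with it for places.

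These points limit the wording. They do not supply the positives that section 2.7 relies on.

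**Conclusion.** The concern holds in a limited form. Read as written, Phase I leaves the number of HIV, HBsAg and anti-HDV positives to chance co-infection while promising sensitivity and AUROC for every virus. For HBsAg, sensitivity would probably be very imprecise: a lower limit of 2.5% to 48% with 1 to 5 positives all detected, and 69% with 10. For anti-HDV it may not be estimable, with a 37% to 61% chance of no positive at an assumed 0.5% to 1%. HIV is less affected. Specificity and the HCV validation are not affected.

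Two things carry this conclusion: the cumulative reading of an incomplete eligibility sentence, and co-infection rates that are assumptions throughout. The point should be settled before Phase I enrolment, because it decides what Phase I and objective 5 can conclude about HBV and HDV.

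**What to change.** **Section 2.3, Phase I.** Complete the eligibility sentence. State that HCV-RNA and genotype results are required only of patients enrolled as HCV positives. Admit known HIV- or HBsAg-positive patients with recent serology from the hospital for all four viruses, within the same total of 100. Prespecify a minimum number of reference positives per virus, with co-infected patients counting for each virus they carry. The sponsor should choose the minima so that HCV precision and genotype coverage are kept. The wording on consecutive inclusion must be adapted to allow them.

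**Section 2.7, Phase I.** State that sensitivity and AUROC are claimed only for viruses that reach their minimum. For the others, probably HDV, report counts with exact intervals, and label their Phase II prevalence under objective 5 as coming from a card assay whose sensitivity was not established.

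**Cost.** Somewhat fewer HCV positives. With 85 instead of 100, the exact 95% interval near 94% sensitivity is 86.8% to 98.1% (80/85) instead of 87.4% to 97.8% (94/100). Genotypes 1b, 1a and 3 make up 44 + 26 + 20 = 90% of the national distribution quoted in 2.3. The places left for the rest, including genotypes 2 and 4, would fall from about 10 to about 8 or 9 (0.10 × 85 = 8.5). If the minima add up to more than 100, they fit only with enough co-infection. Limiting the claim in 2.7 costs nothing and can be adopted alone.
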